2.2. Baseline and End Point

Baseline is defined for each parameter/assessment.

- Baseline (DB): The last assessment before receiving the first dose of intranasal study medication in the double-blind induction phase.

- Baseline (OL): The last assessment before receiving the first dose of intranasal study medication in the open-label induction phase.

Baseline (DB) will be used for DB induction phase, DB follow-up phase and posttreatment (PT) phase. Baseline (OL) will be used for OL induction phase and OL follow-up phase.

The ‘End Point (DB)’ value is defined as the last post baseline assessment value during the double-blind induction phase.

The ‘End Point (OL)’ value is defined as the last post baseline assessment value during the open-label induction phase.

2.3. Visit Windows

As subjects do not always adhere to the protocol visit schedule (including permitted visit windows), the following rules are applied to assign actual visits to protocol visits. Listed below are the visit windows for analysis and the target days for each visit. The reference day is Study Day 1 (which is the first day that study drug was taken in the double-blind phase).

If a subject has 2 or more scheduled or unscheduled visits in one visit window, the visit closest to the target day will be used as the protocol visit for that visit window. If 2 actual visits are equidistant from the target day within a visit window, the later visit is used. If a visit window has no scheduled visits but does have unscheduled visits, then the unscheduled visit closest to the scheduled visit will be used.

All assignments will be made in chronological order. Once a visit is assigned to a visit window, it will no longer be used for a later time point except for the end point.

Listed below are the visit windows and the target days (if applicable) for each visit defined in the protocol for all phases ([Table 1](#)).

Table 1: Analysis Visits

| Parameter | Analysis Phase | Scheduled Day ^a | Time Interval (label on output) | Time Interval ^d (Day) | Target Time Point ^d (Day) |
|-----------|-----------------------------------|----------------------------|---------------------------------|----------------------------------|--------------------------------------|
| MADRS | Screening /lead-in | | Week -6 (SL) | | |
| | | | Week -4 (SL) | | |
| | | | Week -2 (SL) | | |
| | DB | 1 | Baseline (DB) | ≤1 (predose) | 1 |
| | | 2 | Day 2 (DB) | 2 | 2 |
| | | 8 | Day 8 (DB) | 3-11 | 8 |
| | | 15 | Day 15 (DB) | 12-18 | 15 |
| | | 22 | Day 22 (DB) | 19-25 | 22 |
| | | 28 | Day 28 (DB) | 26 to end of DB | 28 |
| | | DB final visit | End Point (DB) | 2 to end of DB | |
| | DB FU | DB F/U 7 | Week 1 (DB F/U) | DB F/U start day-10 | 7 |
| | | DB F/U 14 | Week 2 (DB F/U) | 11-21 | 14 |
| | | DB F/U 28 | Week 4 (DB F/U) | 22 to end of DB F/U | 28 |
| | | DB F/U final visit | End Point (DB F/U) | 1 to end of DB F/U | |
| | PT ^f Weekly 1 | 32 | Week 1 (PT) | PT start day to 35 | 32 |
| | PT ^f Weekly x=2,3,.... | 25 + x*7 | Week x (PT) | 22 + x*7 to 28 + x*7 | 25 + x*7 |
| | OL | OL 1 | Baseline (OL) | ≤1 (predose) | 1 |

Table 1: Analysis Visits

| Parameter | Analysis Phase | Scheduled Day ^a | Time Interval (label on output) | Time Interval ^a (Day) | Target Time Point ^a (Day) | |
|-----------|--------------------|----------------------------|---------------------------------|----------------------------------|--------------------------------------|----|
| | | OL 8 | Day 8 (OL) | 2-11 | 8 | |
| | | OL 15 | Day 15 (OL) | 12-18 | 15 | |
| | | OL 22 | Day 22 (OL) | 19-25 | 22 | |
| | | OL 28 | Day 28 (OL) | 26 to end of OL | 28 | |
| | | OL final visit | End Point (OL) | 2 to end of OL | | |
| | OL FU | OL F/U 7 | Week 1 (OL F/U) | OL FU start day-10 | 7 | |
| | | OL F/U 14 | Week 2 (OL F/U) | 11-21 | 14 | |
| | | OL F/U 28 | Week 4 (OL F/U) | 22 to end of OL F/U | 28 | |
| | | OL F/U final visit | End Point (OL F/U) | 1 to end of OL F/U | | |
| POMS-2 | DB | 25 | Day 25 (DB) | 2 to end of DB | 25 | |
| | DB FU | DB F/U 7 | Week 1 (DB F/U) | DB F/U start day-10 | 7 | |
| | | DB F/U 14 | Week 2 (DB F/U) | 11-21 | 14 | |
| | | DB F/U 28 | Week 4 (DB F/U) | 22 to end of DB F/U | 28 | |
| | | DB F/U final visit | End Point (DB F/U) | 1 to end of DB F/U | | |
| | PT | 32 | Week 1 (PT) | PT start day to 35 | 32 | |
| | | 39 | Week 2 (PT) | 36-46 | 39 | |
| | | 53 | Week 4 (PT) | 47-60 | 53 | |
| | | 67 | Week 6 (PT) | 61-74 | 67 | |
| | | 81 | Week 8 (PT) | 75-95 | 81 | |
| | | 109 | Week 12 (PT) | 96-123 | 109 | |
| | | 137 | Week 16 (PT) | 124-151 | 137 | |
| | | 165 | Week 20 (PT) | 152-179 | 165 | |
| | OL FU | OL F/U 7 | Week 1 (OL F/U) | OL FU start day-10 | 7 | |
| | | OL F/U 14 | Week 2 (OL F/U) | 11-21 | 14 | |
| | | OL F/U 28 | Week 4 (OL F/U) | 22 to end of OL F/U | 28 | |
| | | OL F/U final visit | End Point (OL F/U) | 1 to end of OL F/U | | |
| | SDS | DB | 1 | Baseline (DB) | ≤1 (predose) | 1 |
| | | | 28 | Day 28 (DB) | 2 to end of DB | 28 |
| PT | | 39 | Week 2 (PT) | PT start day to 46 | 39 | |
| | | 53 | Week 4 (PT) | 47-60 | 53 | |
| | | 67 | Week 6 (PT) | 61-74 | 67 | |
| | | 81 | Week 8 (PT) | 75-95 | 81 | |
| | | 109 | Week 12 (PT) | 96-123 | 109 | |
| | | 137 | Week 16 (PT) | 124-151 | 137 | |
| | | 165 | Week 20 (PT) | 152-179 | 165 | |
| | | 193 | Week 24 (PT) | 180 to end of PT | 193 | |
| CGI-S | Screening /lead-in | | Week -6 (SL) | | | |
| | | | Week -4 (SL) | | | |
| | | | Week -2 (SL) | | | |
| | DB | 1 | Baseline (DB) | ≤1 (predose) | 1 | |
| | | 8 | Day 8 (DB) | 2-11 | 8 | |
| | | 15 | Day 15 (DB) | 12-18 | 15 | |
| | | 22 | Day 22 (DB) | 19-25 | 22 | |
| | | 28 | Day 28 (DB) | 26 to end of DB | 28 | |
| | | DB final visit | End Point (DB) | 2 to end of DB | | |
| | DB FU | DB F/U 7 | Week 1 (DB F/U) | DB F/U start day-10 | 7 | |
| | | DB F/U 14 | Week 2 (DB F/U) | 11-21 | 14 | |
| | | DB F/U 28 | Week 4 (DB F/U) | 22 to end of DB F/U | 28 | |
| | | DB F/U final visit | End Point (DB F/U) | 1 to end of DB F/U | | |
| | PT | 32 | Week 1 (PT) | PT start day to 35 | 32 | |
| | | 39 | Week 2 (PT) | 36-42 | 39 | |
| | | 46 | Week 3 (PT) | 43-49 | 46 | |
| | | 53 | Week 4 (PT) | 50-60 | 53 | |
| | | 67 | Week 6 (PT) | 61-74 | 67 | |
| | | 81 | Week 8 (PT) | 75-95 | 81 | |
| | | 109 | Week 12 (PT) | 96-123 | 109 | |
| | | 137 | Week 16 (PT) | 124-151 | 137 | |
| | | 165 | Week 20 (PT) | 152-179 | 165 | |
| | | 193 | Week 24 (PT) | 180 to end of PT | 193 | |
| | OL | OL 1 | Baseline (OL) | ≤1 (predose) | 1 | |
| | | OL 8 | Day 8 (OL) | 2-11 | 8 | |
| | | OL 15 | Day 15 (OL) | 12-18 | 15 | |

Table 1: Analysis Visits

| Parameter | Analysis Phase | Scheduled Day ^a | Time Interval (label on output) | Time Interval ^a (Day) | Target Time Point ^a (Day) | |
|---|--------------------|----------------------------|--|--|--------------------------------------|----|
| | | OL 22 | Day 22 (OL) | 19-25 | 22 | |
| | | OL 28 | Day 28 (OL) | 26 to end of OL | 28 | |
| | | OL final visit | End Point (OL) | 2 to end of OL | | |
| | OL FU | OL F/U 7 | Week 1 (OL F/U) | OL FU start day-10 | 7 | |
| | | OL F/U 14 | Week 2 (OL F/U) | 11-21 | 14 | |
| | | OL F/U 28 | Week 4 (OL F/U) | 22 to end of OL F/U | 28 | |
| | | OL F/U final visit | End Point (OL F/U) | 1 to end of OL F/U | | |
| GAD-7 | DB | 1 | Baseline (DB) | ≤1 (predose) | 1 | |
| | | 15 | Day 15 (DB) | 2-21 | 15 | |
| | | 28 | Day 28 (DB) | 22 to end of DB | 28 | |
| | | DB final visit | End Point (DB) | 2 to end of DB | | |
| Vital Signs (TEMP [predose at each visit], BP ^b , PULSE, RESP [at each visit, predose, 40M, 1H, 1.5H]) | Screening /lead-in | | Week -10 (SL) | | | |
| | | | Week -6 (SL) | | | |
| | | | Week -4 (SL) | | | |
| | DB | 1 | Baseline (DB) Day 1: 40M (DB) Day 1: 1H (DB) Day 1: 1.5H (DB) | ≤ 1 / predose | 1 | |
| | | 4 | Day 4: Predose (DB) Day 4: 40M (DB) Day 4: 1H (DB) Day 4: 1.5H (DB) | 2-6 | 4 | |
| | | 8 | Day 8: Predose (DB) Day 8: 40M (DB) Day 8: 1H (DB) Day 8: 1.5H (DB) | 7-9 | 8 | |
| | | 11 | Day 11: Predose (DB) Day 11: 40M (DB) Day 11: 1H (DB) Day 11: 1.5H (DB) | 10-13 | 11 | |
| | | 15 | Day 15: Predose (DB) Day 15: 40M (DB) Day 15: 1H (DB) Day 15: 1.5H (DB) | 14-16 | 15 | |
| | | 18 | Day 18: Predose (DB) Day 18: 40M (DB) Day 18: 1H (DB) Day 18: 1.5H (DB) | 17-20 | 18 | |
| | | 22 | Day 22: Predose (DB) Day 22: 40M (DB) Day 22: 1H (DB) Day 22: 1.5H (DB) | 21-23 | 22 | |
| | | 25 | Day 25: Predose (DB) Day 25: 40M (DB) Day 25: 1H (DB) Day 25: 1.5H (DB) | 24 to end of DB | 25 | |
| | | DB final visit | End Point (DB) | Day 1: 40M to end of DB | | |
| | | OL | OL 1 | Baseline (OL) Day 1: 40M (OL) Day 1: 1H (OL) Day 1: 1.5H (OL) | ≤ 1 / predose | 1 |
| | | | OL 4 | Day 4: Predose (OL) Day 4: 40M (OL) Day 4: 1H (OL) Day 4: 1.5H (OL) | 2-6 | 4 |
| | | | OL 8 | Day 8: Predose (OL) Day 8: 40M (OL) Day 8: 1H (OL) Day 8: 1.5H (OL) | 7-9 | 8 |
| | | | OL 11 | Day 11: Predose (OL) Day 11: 40M (OL) Day 11: 1H (OL) Day 11: 1.5H (OL) | 10-13 | 11 |
| | OL 15 | | Day 15: Predose (OL) Day 15: 40M (OL) Day 15: 1H (OL) Day 15: 1.5H (OL) | 14-16 | 15 | |

Table 1: Analysis Visits

| Parameter | Analysis Phase | Scheduled Day ^a | Time Interval (label on output) | Time Interval ^a (Day) | Target Time Point ^a (Day) |
|-----------------------------|--------------------|----------------------------|--|----------------------------------|--------------------------------------|
| | | OL 18 | Day 18: Predose (OL) Day 18: 40M (OL) Day 18: 1H (OL) Day 18: 1.5H (OL) | 17-20 | 18 |
| | | OL 22 | Day 22: Predose (OL) Day 22: 40M (OL) Day 22: 1H (OL) Day 22: 1.5H (OL) | 21-23 | 22 |
| | | OL 25 | Day 25: Predose (OL) Day 25: 40M (OL) Day 25: 1H (OL) Day 25: 1.5H (OL) | 24 to end of DB | 25 |
| | | OL final visit | End Point (OL) | Day 1: 40M to end of OL | |
| Weight and BMI | DB | Screening, 1 | Baseline (DB) | ≤ 1 / predose | 1 |
| | | 15 | Day 15 (DB) | 2-21 | 15 |
| | | 28 | Day 28 (DB) | 22 to end of DB | 28 |
| | | DB final visit | End Point (DB) | 2 to end of DB | |
| | OL | OL 1 | Baseline (OL) | ≤ 1 / predose | 1 |
| | | OL 15 | Day 15 (OL) | 2-21 | 15 |
| | | OL 28 | Day 28 (OL) | 22 to end of OL | 28 |
| | | OL final visit | End Point (OL) | 2 to end of OL | |
| ECG | DB | Screening, 1 | Baseline (DB) | ≤ 1 / predose | 1 |
| | | 1 | Day 1: 1H (DB) | 1 | 1 |
| | | 8 | Day 8: 1H (DB) | 2-11 | 8 |
| | | 15 | Day 15: 1H (DB) | 12-20 | 15 |
| | | 25 | Day 25: 1H (DB) | 21 to end of DB | 25 |
| | DB final visit | End Point (DB) | 2 to end of DB | | |
| | OL | OL 1 | Day 1: 1H (OL) | 1 | 1 |
| | | OL 15 | Day 15: 1H (OL) | 2-20 | 15 |
| OL 25 | | Day 25: 1H (OL) | 21 to end of OL | 25 | |
| OL final visit | End Point (OL) | 2 to end of OL | | | |
| Lab (Hematology, Chemistry) | Screening /lead-in | | Screening | | |
| | DB | Screening, 1 | Baseline (DB) | ≤ 1 / predose | 1 |
| | | 28 | Day 28 (DB) | 2 to end of DB | 28 |
| | OL | OL 1 | Baseline (OL) | ≤ 1 / predose | 1 |
| | | OL 28 | Day 28 (OL) | 2 to end of OL | 28 |
| | C-SSRS | Screening /lead-in | | Week -10 (SL) | |
| | | | Week -6 (SL) | | |
| | | | Week -4 (SL) | | |
| | | | Week -2 (SL) | | |
| | | | | | |
| DB | | 1 | Baseline (DB) | ≤1 (predose) | 1 |
| | | 4 | Day 4 (DB) | 2-6 | 4 |
| | | 8 | Day 8 (DB) | 7-9 | 8 |
| | | 11 | Day 11 (DB) | 10-13 | 11 |
| | | 15 | Day 15 (DB) | 14-16 | 15 |
| | | 18 | Day 18 (DB) | 17-20 | 18 |
| | | 22 | Day 22 (DB) | 21-23 | 22 |
| | | 25 | Day 25 (DB) | 24-26 | 25 |
| | | 28 | Day 28 (DB) | 27 to end of DB | 28 |
| | | DB final visit | End Point (DB) | 2 to end of DB | |
| | | DB FU | DB F/U 7 | Week 1 (DB F/U) | DB F/U start day-10 |
| DB F/U 14 | | | Week 2 (DB F/U) | 11-21 | 14 |
| DB F/U 28 | | | Week 4 (DB F/U) | 22 to end of DB F/U | 28 |
| DB F/U final visit | | | End Point (DB F/U) | 1 to end of DB F/U | |
| PT | | 32 | Week 1 (PT) | PT start day to 35 | 32 |
| | | 39 | Week 2 (PT) | 36-42 | 39 |
| | | 46 | Week 3 (PT) | 43-49 | 46 |
| | | 53 | Week 4 (PT) | 50-60 | 53 |
| | | 67 | Week 6 (PT) | 61-74 | 67 |
| | | 81 | Week 8 (PT) | 75-95 | 81 |
| | | 109 | Week 12 (PT) | 96-123 | 109 |
| | | 137 | Week 16 (PT) | 124-151 | 137 |
| | 165 | Week 20 (PT) | 152-179 | 165 | |

Table 1: Analysis Visits

| Parameter | Analysis Phase | Scheduled Day ^a | Time Interval (label on output) | Time Interval ^a (Day) | Target Time Point ^a (Day) |
|--|----------------|----------------------------|---------------------------------|----------------------------------|--------------------------------------|
| | OL | 193 | Week 24 (PT) | 180 to end of PT | 193 |
| | | OL 1 | Baseline (OL) | ≤1 (predose) | 1 |
| | | OL 4 | Day 4 (OL) | 2-6 | 4 |
| | | OL 8 | Day 8 (OL) | 7-9 | 8 |
| | | OL 11 | Day 11 (OL) | 10-13 | 11 |
| | | OL 15 | Day 15 (OL) | 14-16 | 15 |
| | | OL 18 | Day 18 (OL) | 17-20 | 18 |
| | | OL 22 | Day 22 (OL) | 21-23 | 22 |
| | | OL 25 | Day 25 (OL) | 24-26 | 25 |
| | | OL 28 | Day 28 (OL) | 27 to end of OL | 28 |
| | OL final visit | End Point (OL) | 2 to end of OL | | |
| | OL FU | OL F/U 7 | Week 1 (OL F/U) | OL FU start day-10 | 7 |
| | | OL F/U 14 | Week 2 (OL F/U) | 11-21 | 14 |
| | | OL F/U 28 | Week 4 (OL F/U) | 22 to end of OL F/U | 28 |
| OL F/U final visit | | End Point (OL F/U) | 1 to end of OL F/U | | |
| MOAA/S ^c Oxygen Saturation ^d (predose and every 15 minutes to 1.5H) BPRS+ and CADSS (predose, 40M, 1.5H) CGADR ^e (1H, 1.5H) | DB | 1 | Baseline (DB) | ≤1 | 1 |
| | | 4 | Day 4 (DB) | 2-6 | 4 |
| | | 8 | Day 8 (DB) | 7-9 | 8 |
| | | 11 | Day 11 (DB) | 10-13 | 11 |
| | | 15 | Day 15 (DB) | 14-16 | 15 |
| | | 18 | Day 18 (DB) | 17-20 | 18 |
| | | 22 | Day 22 (DB) | 21-23 | 22 |
| | | 25 | Day 25 (DB) | 24 to end of DB | 25 |
| | | DB final visit | End Point (DB) | 2 to end of DB | |
| | OL | OL 1 | Baseline (OL) | ≤1 (predose) | 1 |
| | | OL 4 | Day 4 (OL) | 2-6 | 4 |
| | | OL 8 | Day 8 (OL) | 7-9 | 8 |
| | | OL 11 | Day 11 (OL) | 10-13 | 11 |
| | | OL 15 | Day 15 (OL) | 14-16 | 15 |
| | | OL 18 | Day 18 (OL) | 17-20 | 18 |
| | | OL 22 | Day 22 (OL) | 21-23 | 22 |
| | | OL 25 | Day 25 (OL) | 24 to end of OL | 25 |
| | | OL final visit | End Point (OL) | 2 to end of OL | |
| PWC-20 | DB | 25 | Day 25 (DB) | 2 to end of DB | 25 |
| | | DB F/U | DB F/U 7 | Week 1 (DB F/U) | DB F/U start day-10 |
| | DB F/U | DB F/U 14 | Week 2 (DB F/U) | 11-21 | 14 |
| | | DB F/U 28 | Week 4 (DB F/U) | 22 to end of DB F/U | 28 |
| | | DB F/U final visit | End Point (DB F/U) | 1 to end of DB F/U | |
| | PT | 32 | Week 1 (PT) | PT start day to 35 | 32 |
| | | 39 | Week 2 (PT) | 36-42 | 39 |
| | | 46 | Week 3 (PT) | 43-49 | 46 |
| | | 53 | Week 4 (PT) | 50-60 | 53 |
| | | 67 | Week 6 (PT) | 61-74 | 67 |
| | | 81 | Week 8 (PT) | 75-95 | 81 |
| | OL | OL 25 | Day 25 (OL) | 2 to end of OL | 25 |
| | OL FU | OL F/U 7 | Week 1 (OL F/U) | OL FU start day-10 | 7 |
| | | OL F/U 14 | Week 2 (OL F/U) | 11-21 | 14 |
| | | OL F/U 28 | Week 4 (OL F/U) | 22 to end of OL F/U | 28 |
| OL F/U final visit | | End Point (OL F/U) | 1 to end of OL F/U | | |
| Pharmacokinetics | DB | 4 | Day 4 (DB) | 2-6 | 4 |
| | | 25 | Day 25 (DB) | 24 to end of DB | 25 |
| | OL | OL 25 | Day 25 (OL) | 24 to end of OL | 25 |

^a For DB and posttreatment phases, the time interval is relative to the first day of DB phase. For other phases, the time interval is relative to the first day of that phase.

^b During the DB phase, at 1.5 hours post dose if the SBP is ≥160 and/or DBP≥100, assessments should continue every 30 minutes until the blood pressure is <160 and/or <100 or investigator's clinical judgment the subject is clinically stable and can be discharged from the clinical site or subject is referred for appropriate medical care, if clinically indicated or the blood pressure remains ≥180 mm Hg SBP or ≥110 mm Hg DBP or both, 2 hours after dosing, the subject should be referred for immediate medical treatment.

^c If the MOAA/S score is ≤ 3 at any time during the 1.5 hour postdose interval, the MOAA/S will be performed every 5 minutes until a score of 4 is reached (at which point a frequency of every 15 minutes can be resumed until t=+1.5 hours post dose).

^d If pulse oximetry is <93% at any time during the 1.5 hour postdose interval, pulse oximetry will be performed every 5 minutes until oxygen saturation returns to ≥93% or until the subject is referred for appropriate medical care, if clinically indicated.

^e If the response is not "Yes" at 1.5 hour postdose, the assessment will be repeated every 15 minutes until a "Yes" response is achieved or until the subject is referred for appropriate medical care if clinically indicated.

^f In the posttreatment phase, MADRS assessments will be performed weekly through Week 24 or relapse, whichever occurs first.

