Instructions for use documents (healthcare provider versions) for intranasal study drug administration will be provided as separate documents. Details regarding study drug administration will be recorded in the source documents and the eCRF. In the event of a missed dose, ensure to contact to sponsor immediately.

Prior to the first intranasal dose on Day 1, subjects will practice spraying (into the air, not intranasally) with a demonstration intranasal device that is filled with placebo solution.

The intranasal treatment sessions (esketamine or placebo) will occur twice weekly. Subjects will self-administer the intranasal study drug (esketamine 28 mg, 56 mg, 84 mg, or placebo) at treatment sessions occurring twice a week for 4 weeks at the study-site. The first treatment session will be on Day 1. Intranasal treatment sessions should not take place on consecutive days.

To improve tolerability, subjects who will be randomly assigned to esketamine 84 mg will start at 56 mg on Day 1 and then the dose will increase to 84 mg on Day 4 as a forced titration and remain at 84 mg for all subsequent intranasal treatment sessions. Subjects who are randomly assigned to 28 mg and 56 mg dose groups will remain on that dose for all subsequent intranasal treatment sessions. No adjustment to the intranasal esketamine dose is permitted for the duration of the double-blind induction phase.

Food will be restricted for at least 2 hours before each administration of study drug. Drinking of any fluids will be restricted for at least 30 minutes before the first nasal spray.

If the subject has nasal congestion on the dosing day, an intranasal decongestant can be used to reduce congestion or the dosing day be delayed (per the permitted visit window; see the Time and Events Schedules). If an intranasal decongestant is used to reduce congestion, it cannot be used within 1 hour prior to intranasal study drug administration.

On all intranasal treatment sessions, subjects must remain at the clinical site until study procedures have been completed and the subject is ready for discharge. Subjects should be

accompanied by a responsible adult when released from the clinical study site. Subjects must not drive a car or work with machines for 24 hours after the intranasal treatment session.

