6.3.1. Guidance on Blood Pressure Monitoring on Intranasal Treatment Session Days

Given the potential for treatment-emergent transient elevation in SBP and DBP, the following guidance should be followed on intranasal dosing days:

- If subsequent to fulfilling the inclusion and exclusion criteria on Day 1 (ie, applicable for all other intranasal treatment session days after Day 1), a subject's predose SBP is >140 mm Hg or DBP is >90 mm Hg or both, it is recommended to repeat the blood pressure measurement after subject rests in sitting or recumbent position. If after rest and repeated measurements, predose SBP is >140 mm Hg or DBP is >90 mm Hg or both (except for Day 1), then dosing should be postponed and the subject must be scheduled to return on the following day or within the given visit window (if it is shown on Day 1, the subject should be excluded from the study). If the blood pressure elevation still persists on the next visit, the subject will be scheduled for a consultation by cardiologist, other specialist, or primary care physician, prior to further dosing.
- If at any postdose time point on the dosing day, the SBP is ≥ 180 mm Hg but <200 mm Hg or the DBP is ≥ 110 mm Hg but <120 mm Hg or both, further intranasal dosing should be interrupted and the subject should be referred to a cardiologist, other specialist, or primary care physician for a follow-up assessment.
 - After the assessment by a cardiologist, other specialist, or primary care physician, if recommended by the referring doctor and considered appropriate according to the clinical judgment for the subject to continue in the study, the subject may continue with intranasal dosing if the predose blood pressure at the next scheduled visit is within the acceptable range (see bullet point above).
- If at any postdose time point on the dosing day the SBP is ≥ 200 mm Hg or the DBP is ≥ 120 mm Hg or both, the subject must discontinue from further dosing and the subject should be referred to a cardiologist, other specialist, or primary care physician for a follow-up assessment.

During the double-blind induction phase, at 1.5 hours postdose, if the SBP is ≥ 160 mm Hg or the DBP ≥ 100 mm Hg or both, assessments should continue every 30 minutes until:

- Blood pressure is <160 mm Hg SBP and <100 mm Hg DBP, or
- In the investigator's clinical judgment, the subject is clinically stable and can be discharged from the study-site, or

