5.3. Vital Signs, Weight, and BMI

Descriptive statistics (N, mean, median, minimum, and maximum) for values and changes from baseline at each time point during each induction phase (DB and OL) will be presented for temperature, systolic blood pressure, diastolic blood pressure, pulse rate, respiratory rate, oxygen saturation, weight, and BMI. In addition, descriptive statistics of pulse rate and blood pressure (systolic and diastolic) values, changes and percent changes from predose will be provided for each dosing day. These summaries will also be provided by hypertension status (defined in [Table 2](#), Yes/No). Descriptive statistics for maximum increases and maximum percent increase from predose will be provided for each dosing day. Frequency distributions of maximum percent change increase from predose and time of maximum percent change increase will also be presented. Note that if the maximum value within a phase occurs at multiple time points, the earliest time point is selected.

The proportion of subjects who have a treatment-emergent abnormality, as defined in [Table 5](#) below, during each induction phase will be presented. Both the double-blind/open-label baseline and the predose assessment will be used to determine abnormal values. A listing of subjects meeting any of the criteria will also be provided for each induction phase.

Table 5: Treatment-Emergent Abnormality Categories for Vital Signs

| Vital Parameter | Postbaseline value outside of normal limit if: | |
|----------------------|--|--|
| | Abnormally low | Abnormally high |
| Pulse (bpm) | A decrease from baseline of ≥ 15 to a value ≤ 50 | An increase from baseline of ≥ 15 to a value ≥ 100 |
| Systolic BP (mm Hg) | A decrease from baseline of ≥ 20 to a value ≤ 90 | An increase from baseline of ≥ 20 to a value ≥ 180 |
| Diastolic BP (mm Hg) | A decrease from baseline of ≥ 15 to a value ≤ 50 | An increase from baseline of ≥ 15 to a value ≥ 105 |

The proportion of subjects who experienced acute hypertension (systolic BP \geq 180 or diastolic BP \geq 110) at any time during the study will be summarized by analysis phase, treatment group and hypertension status.

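### SAP 2.3 picks the visit closest to the target day whether or not a dose was given, so when a dose is postponed from a first attempt on or after the target day, change from predose is lost or mispaired

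*SAP*

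**What the plan says.** SAP 2.3 covers the case of several visits in one analysis window: if a subject has "2 or more scheduled or unscheduled visits in one visit window, the visit closest to the target day will be used". On ties: "If 2 actual visits are equidistant from the target day within a visit window, the later visit is used". On re-use: "Once a visit is assigned to a visit window, it will no longer be used for a later time point except for the end point". None of these rules asks whether intranasal drug was given at the visit, and none says whether selection is made for the visit as a whole or separately for each time point.

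Table 1 in the same section puts the predose and postdose vital-sign readings of a session under one day window, for example "Day 8: Predose (DB) Day 8: 40M (DB) Day 8: 1H (DB) Day 8: 1.5H (DB) | 7-9 | 8".

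SAP 5.3 then asks for pulse and blood-pressure values, and "changes and percent changes from predose will be provided for each dosing day", together with maximum increases from predose. SAP 6.2 plots change from predose in SBP, DBP and CADSS total score against plasma concentration.

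The protocol plans for an attendance without a dose. Under 6.3.1, if predose pressure after Day 1 stays above 140 systolic or 90 diastolic on repeat measurement, "then dosing should be postponed and the subject must be scheduled to return on the following day or within the given visit window". Section 6.3 adds that with nasal congestion "an intranasal decongestant can be used to reduce congestion or the dosing day be delayed", and section 4.4 delays dosing within the visit window if the subject appears intoxicated.

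**The concern.** A postponed session leaves two attendances: one with predose readings only, and a later one with predose readings, the dose and postdose readings. A rule based only on distance from the target day can choose the first.

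- **Selection by visit:** the postdose readings belong to the visit not chosen, so that session has no change from predose in the by-day tables.
- **Selection by time point:** the predose value comes from the undosed day, and any postdose values come from another day.

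For postponements caused by blood pressure the error has a direction. The pressure that triggered the delay was above its limit on the undosed day, and dosing follows only once it has come down. Subtracting the undosed reading understates the rise after the dose, and dropping the session removes it. The blood-pressure effect is a named safety interest of this trial. Oxygen saturation, MOAA/S, CADSS and BPRS+ share the gap, since Table 1 gives them the same day windows and they also have predose readings.

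**Working it through.** No figure in the plan bears on this, so there is nothing to reproduce first. The check applies the stated rule to the stated windows.

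**Inputs.** Double-blind vital-sign windows from SAP Table 1; closest visit to target, ties to the later visit (SAP 2.3); clinic visit window of ±1 day for Days 4 to 25 (Protocol, Time and Events Schedule 1); dose given one day after the first attempt (Protocol 6.3.1). I assume that the undosed attendance is recorded as a visit with its predose readings.

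**Visit selected.** With target T, compare |visit day − T| for the two attendances.

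| T | Window | Attempt T−1, dose T (1 v 0) | Attempt T, dose T+1 (0 v 1) | Attempt T+1, dose T+2 (1 v 2) |
|---|---|---|---|---|
| 4 | 2-6 | dosed | undosed | undosed |
| 8 | 7-9 | dosed | undosed | undosed; dose on Day 10 |
| 11 | 10-13 | dosed | undosed | undosed |
| 15 | 14-16 | dosed | undosed | undosed; dose on Day 17 |
| 18 | 17-20 | dosed | undosed | undosed |
| 22 | 21-23 | dosed | undosed | undosed; dose on Day 24 |
| 25 | 24 to end | dosed | undosed | undosed |

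The dosed visit is selected in 7 of 21 cases and the undosed visit in 14 of 21. These count scenarios, not frequencies. The third column lies outside ±1 day, but 6.3.1 allows it by naming the following day as an alternative to the visit window.

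Days 10, 17 and 24 belong to the next session's window (Day 11, 18 or 25). There the postponed dose loses to a next session held on target. It also loses to one held a day after target, because that is a tie and the later visit wins. Its own session then has no postdose values under either way of selecting.

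**Effect on one session (assumed readings).** Undosed-day predose SBP 150, dosed-day predose 130, 40-minute value 145.
- Same session: 145 − 130 = +15 mm Hg.
- By time point under the present rule: 145 − 150 = −5 mm Hg.
- By visit under the present rule: missing.

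**How often (assumed).** The documents give no postponement rate. I simulated a normal predose SBP with a Day 1 reading of at most 140. A session is postponed if SBP is above 140 on target and dosed the next day if it is at most 140. One mean is 122, a plain assumption. The other comes from Panel B in Protocol 1.1.2.3, as peak minus mean increase: 116.4 − 1.7 = 114.7, 124.9 − 6.5 = 118.4 and 125.4 − 7.2 = 118.2. Weighted by 21, 11 and 9 subjects, this gives about 116.5.

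| Between-, within-subject SD | Mean 116.5: share, mismatch | Mean 122: share, mismatch |
|---|---|---|
| 10, 6 | 1.1%, 11.8 mm Hg | 2.5%, 11.4 mm Hg |
| 12, 8 | 2.4%, 15.4 mm Hg | 4.3%, 14.9 mm Hg |
| 12, 10 | 3.6%, 19.1 mm Hg | 5.9%, 18.4 mm Hg |

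Of 183 × 7 = 1,281 sessions after Day 1, this is about 14-46 at mean 116.5 and about 33-75 at mean 122. The esketamine groups have 3 × 37 = 111 subjects and 777 such sessions. At mean 116.5, about 9-28 of these are affected, or 0.4-1.3 subjects per dose group per dosing day. For scale, the mean SBP increase after the first 56 mg dose in Panel B was 7.2 mm Hg, less than any mismatch in the table.

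**The case against.** The strongest reply is that the SAP does not prescribe a wrong subtraction. SAP 5.3 speaks of each dosing day, SAP 5.5 ties CADSS and BPRS+ to each dose and MOAA/S to dosing days, and the protocol sets time 0 at the first spray. A day without a spray is arguably not a dosing day, and a careful programmer would pair values within the dosed session. That is a fair reading of the intent. But no text states it or lets it override SAP 2.3 and Table 1, and two programmers could differ.

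Several stronger readings are tempting, and the documents do not support them:

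- **Every one-day postponement goes wrong.** It does not: with a first attempt one day early, the dosed visit is on target and is selected in all seven windows.
- **ECG and discharge readiness (CGADR) have the same fault.** No predose ECG is required at these sessions and CGADR is only postdose, so an undosed day yields no scheduled record to select wrongly.
- **The error is concentrated in the hypertension rows.** That was not computed. Hypertension status is defined from readings before the double-blind phase.
- **It strikes exactly the subjects with the highest pressures.** Where the elevation persists at the next visit, 6.3.1 requires a consultation before further dosing, so there may be no next-day session to mispair.

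The simulation is also only a guide. It uses one SBP reading where 6.3.1 asks for repeats, and it ignores dropout, which overstates the count. It leaves out DBP and delays for other reasons, which understates it. It places every first attempt on target.

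**Conclusion.** The point holds, within limits. For sessions after Day 1 first attempted on or after the target day and dosed the next day, the stated rule selects the undosed visit. Change from predose is then missing or taken across two days. For delays triggered by blood pressure this understates or removes the rise in the pressure that caused the delay.

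The affected outputs are descriptive: change and maximum increase from predose by dosing day (SAP 5.3), the predose-based part of the treatment-emergent abnormality table, and the SBP, DBP and CADSS change-from-predose plots (SAP 6.2). A reader might infer that the blood-pressure safety conclusions as a whole, or efficacy, are at risk. They are not: acute hypertension at any time needs no predose value, the abnormality table also uses the phase baseline, and the efficacy analyses do not depend on these readings.

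The size rests on assumed pressures: about 1-6% of sessions, with a mismatch of about 11-19 mm Hg. Overall means move little, but in an affected session the computed change can be zero or negative. That the rule selects the undosed visit follows from the text and needs no assumption about pressure, only that the undosed attendance is recorded as a visit.

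**What to change.** Add to SAP 2.3, for parameters measured both before and after dosing at a session (vital signs, oxygen saturation, MOAA/S, CADSS, BPRS+):

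- Values are assigned to the dosing session they belong to, using the dosing record.
- Predose is the last reading before that session's dose on the same day. This applies also when the dose falls in the day window of the next session.
- Readings from visits without a dose are listed and are not used as the predose value.

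Leave the closest-to-target rule for ECG, CGADR, undosed Early Withdrawal visits and all other parameters. The ECG windows in particular span several dosing days (Day 8 covers Days 2-11), so a dosed-visit condition would not identify a single visit there.

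Under this wording all 21 scenarios above use the dosed session, against 7 of 21 now. The cost is a short SAP addition and a link to dosing data that the protocol already has recorded in the eCRF. It needs no new data and leaves the postponement rule in the protocol as it is.
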